## 14.3 E-selectin studies (Alliance A041701-LC1)

### 14.3.1 Background

E-selectin mediated interactions may play a role in AML and the expression of E-selectin or its binding epitope (sialyl  $Le^{a/x}$ ) may predict the clinical course and patient outcomes in AML. Increased expression of E-selectin, as seen in inflammatory conditions, malignant states such as leukemia, and during chemotherapy, is also associated with increased shedding of E-selectin from the cell surface resulting in higher levels of sE-selectin in the circulation.

We will measure the levels of E-selectin ligand on pretreatment bone marrow blasts in patients treated with or without uproleselan to describe the cell-surface expression pattern of E-selectin ligand on AML blasts and to determine the effect on clinical outcomes. We will also examine plasma sE-selectin at baseline and after treatment with chemotherapy with or without uproleselan to determine if E-selectin inhibition affects sE-selectin levels and to correlate plasma levels with clinical outcomes.

E-selectin (E-sel) is a cell adhesion glycoprotein that is expressed on endothelial cells and has been implicated in therapeutic resistance. In most myeloid leukemias, leukemic blasts express E-selectin ligands, which contain the glycan epitope of the carbohydrate sialyl  $Le^x$  ( $sLe^x$ ). This sequestration in the bone marrow vascular niche, leading to cell adhesion-mediated drug resistance and resultant poor clinical outcome. Uproleselan is an E-selectin antagonist which interrupts leukemic cell homing to the vascular niche, increases susceptibility to cytotoxic and targeted therapies and can be a potent adjunct to therapeutics. In deed data has demonstrated a correlation between leukemic cell surface

levels of E-selectin ligands using multiparameter flow cytometry and response to uproleselan.

Recently, transcriptome profiling of E-selectin ligand-forming glycosylation genes have been explored from public data sets to identify elevated E-selectin ligand expression in patients with AML. RNA-seq data from patients treated in COG AAML1031 ( $N = 1,074$ ) was available for evaluation. Of 24 genes examined, Fucosyltransferase 7 (FUT7) and ST3 beta-galactoside alpha-2,3-sialyltransferase 4 (ST3GAL4) were significantly associated with adverse outcome ( $HR = 1.013, p < 0.0001$ , and  $HR = 1.023, p < 0.0001$ , respectively), and directly synthesize sLex. Patients highly expressing *FUT7* (highest quartile of expression) had significantly worse outcome than lower expressors (lowest 3 quartiles of expression), with a 5-year OS of 50.3% vs. 68.3% ( $p < 0.0001$ ). Similarly, those with high *ST3GAL4* expression had a 5-year OS of 51.3%, compared to 68.1% for low expressors ( $p < 0.0001$ ). High expression of these genes was shown to be associated with cell surface E-selectin ligand expression. Taken together these data suggest a strong correlation between transcriptome measurements of E-selectin ligand-forming glycosylation genes and cell surface glycosylation levels of E-selectin ligands, and lend support for the use of E-selectin ligand glycosylation genes as predictive biomarkers.

We will measure the expression of E-selectin ligand-forming glycosylation genes from pretreatment bone marrow blasts treated with or without uproleselan to describe the RNA expression levels of these genes on AML blasts and to determine the effect on clinical outcomes.

Traditional measures of response in AML rely on the morphological characterization of blasts after therapy with complete remissions requiring less than 5% blasts to be present in the bone marrow. The morphological determination of blasts lacks sensitivity to identify low levels of residual disease and is subject to both sampling and interpretation error. Measurable residual disease (MRD) denotes the presence of leukemia cells down to levels of  $1:10^4$  to  $1:10^6$  white blood cells (WBCs), compared with 1:20 in morphology-based assessments. Multiple studies have demonstrated that the achievement of a negative MRD status is associated with improved clinical outcomes. In this study, we will utilize a flow cytometry-based MRD assessment at the end of induction and consolidation to explore potential differences in the experimental and control arms and correlate these results with clinical outcomes.

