## 5.0 STUDY CALENDAR

The pre-study testing intervals are guidelines only. Laboratory and clinical parameters during treatment are to be followed using individual institutional guidelines and the best clinical judgment of the responsible physician. It is expected that patients on this study will be cared for by physicians experienced in the treatment and supportive care of patients on this trial.

When calculating days of tests and measurements, the day a test or measurement is done is considered Day 0. Therefore, if a test were done on a Monday, the Monday one week later would be considered Day 7.

	Baseline*	Induction	End of Induction	Consolidation	End of Treatment	Follow-up**
Tests & Observations						
History and physical	X	X		X	X	X
Performance Status	X					
Height and weight	X	X		X		
MUGA or ECHO	X					
ECG	X					
Adverse Event Assessment	X	X	X	X	X	
Laboratory Studies						
FLT3 Mutation analysis	X					
CBC with differential	X	X(2)	X	X(2)		X
Serum Creatinine	X	X(3)		X(3)		
Bilirubin, AST, ALT, Alk. Phos.	X	X(3)		X(3)		
INR, PTT, fibrinogen	X					
Uric Acid	X					
LDH	X					
Molecular genetic testing	X(1)					
Cytogenetics	X		B		B	B
Staging						
BM biopsy/aspirate	X(4)	A	X		X	C
Correlative studies: For patients who consent to participate						
Bone marrow and blood samples	Prior to treatment, end of induction, end of consolidation, and relapse. See Section 6.2.					

\* Baseline studies are to be completed  $\leq$  14 days prior to registration.

\*\* Follow-up should occur at least every 2 months (+/- 14 days) in year 1, every 3 months (+/- 14 days) in year 2, then every 6 months (+/- 30 days) until 5 years from registration (See [Section 12.3](#)). Cytogenetics reports for applicable time points should be submitted until 15 years following registration.

- 1 Molecular testing is to be performed according institutional standards but should include testing for mutations in *FLT3*, *NPM1*, *CEBPA*, *RUNX1*, *ASXL1*, *IDH1*, *IDH2* and *TP53* to allow classification of patients by 2017 WHO criteria and stratification by 2017 ELN genetic risk classification [23].
- 2 CBC should be performed daily while inpatient and at least twice weekly until hematopoietic recovery. Please submit induction lab tests and results in Rave from either the labs drawn at the end of the cycle, or the lab that that will correspond to the disease response.

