#### 6.2 Specimen collection and submission

The Alliance A041701 Correlative Science Manual (CSM) contains instructions for specimen collection, processing and shipping. The manual can be found on the BioMS and CTSU websites. Questions regarding the CSM should be addressed to the contacts specified in the manual.

For all patients registered to Alliance A041701: Bone marrow and peripheral blood will be collected and banked for molecular genetic analysis described in [Section 14.2](#).

For patients registered to substudy A041701-LC1 and/or patients who consent to banking: All participating institutions must ask patients for their consent to participate in Alliance A041701-LC1 and the banking of their specimens for future studies, although patient participation is optional. Rationale and methods for the scientific components of these studies are described in Section 14.0. For patients who consent to participate, bone marrow and blood samples will be collected at the following time points for these studies:

	At Pre-registration	End of Induction	End of Consolidation	Relapse	Storage/Shipping conditions	Submit to:
For all patients registered to A041701, submit the following						
Bone marrow aspirate (EDTA/lavender top)	5 mL				Ambient	HEME
Peripheral blood (EDTA/lavender top)	10 mL				Ambient	HEME
For patients registered to A041701-LC1A, submit the following						
Bone marrow aspirate (heparin/green top)	2 mL	2 mL	2 mL		Ambient	Hematologics
Peripheral blood (Na citrate/light blue top)	2.7 mL	2.7 mL			Frozen/dry ice	HEME

For patients who consent to banking B , submit the following						
Bone marrow aspirate (EDTA/lavender top)	5 mL	5 mL	5 mL	5 mL	Ambient	HEME
Peripheral blood (EDTA/lavender top)	10 mL	10 mL	10 mL	10 mL	Ambient	HEME

- 1 Or submit 30 mL peripheral blood (EDTA/lavender top) if marrow inaspirable or if the patient has had a bone marrow aspiration prior to pre-registration and refuses to have another one performed. This peripheral blood is in addition to the 10 mL required prior to treatment.

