### 7.2 Arm 2 Treatment: 7+3 + Uproleselan

#### 7.2.1 Remission Induction

- Uproleselan 800 mg IV, once a day on Day 1, and q12 hours on Days 2-10 (total of 19 doses)
- Daunorubicin 60 mg m^2/day IV Days 2-4 (total dose 180 mg/m^2)
- Cytarabine 100 mg/m^2/day CIVI Days 2-8 (168 hour infusion, total dose 700 mg/m^2)

The first dose of uproleselan will be given 24 hours (+/- 2 hours) prior to the first dose of chemotherapy as a single sentinel dose. On days 2-10, uproleselan will be administered every 12 hours (+/- 1 hour). On days in which both uproleselan and daunorubicin are administered, administer uproleselan approximately 2 hours (+/- 15 minutes) prior to daunorubicin.

During the Remission Induction, a bone marrow examination (aspirate and biopsy) on Day 14 (+3 days) is required in all patients. Recommendations regarding the need for second induction are provided in the table below. Consult with the study chair if there are questions about the need for reinduction.

Bone Marrow Cellularity	Bone Marrow Leukemic Blasts	Action
$\geq$ 20%	$\geq$ 5%	Second remission induction
	< 5%	Do not start second remission induction therapy. Repeat bone marrow biopsy upon count recovery or by Day 42

< 20%	≥ 5%	Repeat bone marrow biopsy in one week, and follow guidelines in table.
	< 5%	Do not start second remission induction therapy. Repeat bone marrow biopsy upon count recovery or by Day 42

Patients with residual disease as indicated above on Day 14 or subsequent biopsy following the first course of induction chemotherapy are eligible to receive a second remission induction course. It is recommended that a second induction course start within 7 days of bone marrow documentation of residual disease but may be delayed based on the clinical status of the patient. Removal of a patient following a single cycle of induction chemotherapy to receive non-protocol therapy is highly discouraged as the results of the day 14 bone marrow (i.e. high cellularity, blast percentage) do not predict the outcome of second remission induction course.

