#### *Pharmacokinetics*

PK evaluations in healthy volunteers showed a dose-linear relationship in mean PK parameters after IV infusion of 2 mg/kg, 5 mg/kg, 10 mg/kg, 20 mg/kg and 40 mg/kg uproleselan. Uroleselan is characterized by a half-life of 1.4-2.5 hours and does not accumulate after doses up to 20 mg/kg BID. Population PK analysis in healthy volunteers and patients with AML demonstrate similar PK profiles, PK parameters, and dose-proportionality. Clearance was found to depend on renal function and have a similar magnitude in both healthy volunteers and in patients with AML. The PK of uproleselan does not appear to be affected when co-administered with chemotherapy.

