### 14.3.3 Methods

E-selectin ligand will be measured on bone marrow blasts using multiparameter flow cytometry using a standardized panel of monoclonal antibodies designed to identify the blast population. The percentage of cells and mean fluorescence intensity will be used to quantify the extent of E-selectin ligand in this population.

sE-Selectin will be measured from plasma samples obtained at baseline and after induction using a commercially available enzyme-linked immunosorbent assay (ELISA) to human E-selectin.

Expression levels of the E-selectin ligand-forming glycosylation genes, Fucosyltransferase 7 (FUT7) and ST3 Beta-Galactoside Alpha-2,3-Sialyltransferase 4 (ST3GAL4), in RNA extracted from residual bone marrow aspirates of patients diagnosed with AML will be determined by reverse transcription quantitative PCR (RT-qPCR).

To determine whether the E-selectin ligand expression is associated with clinical outcomes, descriptive statistics (i.e. mean, median, standard deviation, and range) and graphical methods (i.e. boxplots, jitter plots) will be used to summarize both pre- and post-treatment E-selectin level to understand its distribution in each treatment arm. To evaluate its association to clinical outcomes, two-sample t-tests or Wilcoxon rank-sum tests will be conducted to compare the E-selectin level between those who achieve remission versus not.

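### The LC1 plasma samples show sE-selectin only after uproleselan has cleared, and the planned pre/post test does not compare the arms, so the stated aim is not answered

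*Combined protocol and SAP*

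**What the plan says.** **Aim.** The background to the E-selectin substudy (14.3.1) says: "We will also examine plasma sE-selectin at baseline and after treatment with chemotherapy with or without uproleselan". The purpose given is "to determine if E-selectin inhibition affects sE-selectin levels and to correlate plasma levels with clinical outcomes". The formal list in 14.3.2 is headed as exploratory, and its only sE-selectin entry is correlation with clinical outcomes.

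**Samples.** Section 14.3.3 states: "sE-Selectin will be measured from plasma samples obtained at baseline and after induction". The specimen table in 6.2 agrees: the LC1 citrate tube is drawn at pre-registration and at end of induction only. The study calendar (5.0) gives the correlative time points as "Prior to treatment, end of induction, end of consolidation, and relapse". Optional banked EDTA blood (6.2) has those same four time points, with the first at pre-registration. None falls during dosing.

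**Drug.** In 7.2.1 the last uproleselan dose of first induction is on Day 10. In 7.2.2 the last dose of a second induction is on Day 8 of that course. Section 10.2 says the drug "is characterized by a half-life of 1.4-2.5 hours and does not accumulate after doses up to 20 mg/kg BID".

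**Analysis.** Section 14.3.3 plans summaries and plots of pre- and post-treatment E-selectin within each arm, tests of responders against non-responders, and Cox models stratified by arm, with similar analyses for sE-selectin. For change in sE-selectin it names two-sample t-tests or Wilcoxon rank-sum tests of pre- against post-induction levels.

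**The concern.** The aim asks what E-selectin inhibition does to sE-selectin. Section 10.2 describes the drug as a competitive inhibitor, and 1.4 justifies the dose by exposure and by time above the IC50 and IC90. On that model, inhibition follows concentration, and at the end-of-induction draw there is essentially no drug left.

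What remains to be seen is a later consequence of having been treated. Section 1.2 reports raised sE-selectin in untreated AML and a link between falling levels and durable remission. Section 14.3.1 ties increased shedding to leukaemia, inflammation and chemotherapy. A lower level in the uproleselan arm could therefore reflect better leukaemia clearance, and similar levels would not show that the target was missed during dosing. Section 1.3 reports that an earlier trial took a fall in plasma sE-selectin as evidence of on-target activity, so a reader may expect the same inference here.

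Separately, the change analysis contrasts two times, whereas the aim contrasts two treatments. Chemotherapy and remission alter sE-selectin in both arms, so a pre/post difference says nothing about uproleselan.

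**Working it through.** **Figures in the plan.** No interval from last dose to plasma sample is stated, so there is none to reproduce. Two nearby figures do reproduce:
- Dose totals: 1 + 2 x 9 = 19 for first induction and 1 + 2 x 7 = 15 for second induction.
- Power of 88% in 14.3.3 (375 v 161 patients, effect size 0.3, two-sided 0.05): 88.8% by the noncentral t, and 87.4% for a Wilcoxon test at relative efficiency 0.955. This concerns baseline expression in responders v non-responders. It is not disputed and does not bear on the arm contrast.

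**Inputs.** Half-life 1.4 to 2.5 h (10.2); last dose Day 10 (7.2.1) or Day 8 of a second course (7.2.2). The sample day is an assumption. The nearest guides are the repeat-marrow rule in 7.2.1 (at count recovery, Day 42 at the latest, for patients with under 5% blasts) and the 2-3 weeks to count recovery expected in 10.4. Neither is a blood-draw rule, so Days 14 to 42 are shown.

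**Formula.** With the last dose in the evening and the sample in the morning, hours elapsed = (sample day - last dose day) x 24 - 12. Half-lives elapsed = hours / half-life.

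| Course | Sample day | Hours | Half-lives at 2.5 h | Half-lives at 1.4 h |
|---|---|---|---|---|
| First | 14 | 84 | 34 | 60 |
| First | 17 | 156 | 62 | 111 |
| First | 21 | 252 | 101 | 180 |
| First | 28 | 420 | 168 | 300 |
| First | 42 | 756 | 302 | 540 |
| Second | 21 | 300 | 120 | 214 |
| Second | 28 | 468 | 187 | 334 |
| Second | 42 | 804 | 322 | 574 |

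One hundred half-lives take 100 x 2.5 / 24 = 10.4 days or 100 x 1.4 / 24 = 5.8 days. After first induction that mark is reached at about Day 20.9 or Day 16.3.

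**Remaining drug.** In the least favourable row the fraction left is 2^-33.6, about 8 x 10^-11. As a stress test, assume a half-life of 10 h, four times the upper stated value. Day 14 is then 84 / 10 = 8.4 half-lives out, leaving 2^-8.4, about 0.3%. The conclusion that the drug has cleared does not depend on the exact multiple.

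**The named test.** Let n patients have both samples, with common SD s and within-patient correlation r. The variance of the mean change is 2s²(1 - r)/n; a two-sample test uses 2s²/n. The ratio of true to assumed standard error is √(1 - r): for assumed r of 0.3 to 0.7, this is 0.84 to 0.55. The test ignores the pairing, and correcting that alone would still leave a contrast of times. By comparison, 14.3.4 does name a test by treatment arm for MRD rates; nothing equivalent is named for sE-selectin.

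**The case against.** - **The aim is worded as post-treatment.** The sentence in 14.3.1 speaks of plasma after treatment, and the sampling matches that. This stands: the plan does not promise an on-treatment measurement. The same sentence still gives the effect of inhibition as the thing to be determined, and it is that inference which needs limiting.
- **It is not a formal objective.** Also true. Baseline and post-induction samples do serve the outcome correlation in 14.3.2. This lowers the severity but leaves the analysis gap.
- **Drug clearance does not prove the effect has gone.** A reader might infer that these samples cannot show any effect of inhibition. The documents do not support that: they give neither the turnover of sE-selectin nor the sampling time behind the fall reported in 1.3. Because both randomised arms are sampled, a difference at end of induction would estimate a real effect of adding uproleselan, even if it acts through more remissions.
- **The half-life multiples are soft.** A reader might also take a gap of more than 100 half-lives as true for every patient. It rests on an assumed sample day. The Correlative Science Manual may say more and is not among the documents, and clearance depends on renal function.
- **By-arm analysis is partly planned.** Descriptive summaries by arm are there. The sentence on change in sE-selectin is also garbled enough that one could read it as comparing change between arms. It does not say so, and the arms are not mentioned in it.

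**Conclusion.** The point holds in a limited form. No LC1 plasma sample is taken with drug present: the post-dose sample is about 101 or more half-lives after the last first-induction dose if drawn from Day 21, and about 34-60 on Day 14. The samples can show a residual or downstream difference between randomised arms, which may partly reflect leukaemia clearance. They cannot give direct evidence for or against inhibition during dosing. The named pre/post two-sample test does not estimate even the difference they can show.

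This rests on the stated half-life range and dosing days, on an assumed sample day, and on reading the change analysis as written. Only an exploratory substudy is affected; the trial's primary and secondary endpoints are not. Severity is low.

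**What to change.** - **14.3.3:** replace the pre/post two-sample test with a between-arm comparison of end-of-induction log sE-selectin, adjusted for baseline log sE-selectin (ANCOVA). Report the estimate with its interval and days since last dose. Show levels by arm within remission and non-remission as description only, since remission is a post-randomisation outcome. Give the number of patients with both samples in each arm, because those who die or leave before the second draw do not contribute.
- **14.3.1:** restate the aim as a comparison of sE-selectin after induction between the arms, and say that it gives no direct evidence for or against on-treatment target inhibition. Bring 14.3.2 into line.

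The cost is wording and a short analysis specification using existing samples. The exploratory substudy gives up an on-treatment pharmacodynamic reading. Adding an on-treatment induction sample is no longer practical, because the study is permanently closed to accrual.

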Adhesion of AML blasts to E-selectin initiated up-regulation of pathways critical to leukemia progression that include members of Wnt signaling [10]. The magnitude of this response correlated with expression of E-selectin ligands on blasts. The Wnt pathway is associated with the regulation of cell proliferation, differentiation, and apoptosis in AML and has been identified as a target for therapy. uproleselan inhibits the E-selectin-mediated activation of the Wnt pathway and may improve response in treatment of AML. Similarly, E-selectin is unique among vascular adhesion molecules in being able to directly activate NF- $\kappa$ B. Upstream blockade of E-selectin by uproleselan has been shown to inhibit NF- $\kappa$ B activation [11]. NF- $\kappa$ B signaling was identified as a pathway potentially dampened in AML blasts following uproleselan administration, suggesting that adhesion to E-selectin activates pro-survival NF- $\kappa$ B signaling in AML cells leading to enhanced chemoresistance. Collectively, these results suggest that E-selectin is a key vascular niche component in the bone marrow mediating LSC resistance to chemotherapy.

Expression of E-selectin or its binding epitope (sialyl Lea/x) may predict the clinical course and patient outcomes in AML [12-16]. Soluble E-selectin (sE-selectin) may be shed from the cell membrane and detected by enzyme-linked immunosorbent assay (ELISA) in the peripheral blood. AML is associated with increased vessel density, and sE-selectin release by activated/proliferating endothelial cells in the bone marrow may contribute to increased E-selectin levels in patients with untreated AML [13, 17]. sE-selectin levels were increased in the serum of patients with newly diagnosed AML compared with that in the serum of healthy subjects [12-14]. sE-selectin levels have also been correlated with the extramedullary infiltration of AML cells ( $P<0.001$ ) and predicted the occurrence of relapse of AML ( $P=0.01$ ); sE-selectin

levels at diagnosis of AML predicted low survival ( $P<0.001$ ); and decrease in sE-selectin levels correlated with durable remission of AML [12, 15].

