### 14.3.2 Exploratory Objectives

- To examine the correlation of E-selectin ligand expression of leukemic blasts with clinical outcome.
- To examine the correlation of plasma soluble E-selectin concentrations with clinical outcomes.
- To examine the correlation of MRD after induction and consolidation chemotherapy with clinical outcomes.
- To examine the correlation of E-selectin ligand-forming glycosylation genes of leukemic blasts with clinical outcome.

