Suppose 80% of patients (n=536) enrolled will have a bone marrow sample available for E-selectin analysis. Assuming 375 patients (out of 536 patients) achieving a remission, we will have 88% power to detect an effect size of 0.3 (effect size defined as the difference in mean divided by the standard deviation,  $\delta = |\mu_1 - \mu_2|/\sigma$ ) in baseline E-selectin expression levels between the responders and non-responders at the 0.05 two-sided alpha level; this assumes a remission rate of 70%. Furthermore, to analyze multiple factors related to the probability of achieving CR, logistic regression models will be constructed. For DFS, EFS, and OS, E-selectin level along with other potentially prognostic factors will be examined in multivariable analyses, using Cox regression model, stratified by treatment arm. Similar analyses will be conducted for sE-selectin. Secondary analysis will evaluate the sE-selectin expression level pre- vs. post-induction will be compared using two-sample t-tests or Wilcoxon rank-sum tests, as well as descriptive statistics and graphical methods. Exploratory analysis will be conducted to investigate the optimal cut-point of baseline E-selectin expression level through ROC analysis.

Flow cytometry will be used to assess for MRD by discriminating between normal regenerating hematopoietic cells in the bone marrow and any remaining acute myeloid leukemia (AML) which abnormally expresses cell surface antigens [27]. This technique, termed “Difference from Normal” is based on correlating the quantitative expression of multiple cell surface antigens (gene products) in the specimens using standardized antibody panels. The Difference from Normal approach identifies all the normal regenerating cells within the specimen first, subtracts them away and then detects clusters of abnormal cells within the remaining data set. Using this technique, it is possible to define the precise composition of the specimen, identifying cells of all lineages and maturational stages as well as assessing specimen quality in addition to detecting and quantifying any abnormal cell population [28].

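### The E-selectin substudy asks whether uproleselan changes plasma sE-selectin, but plans no between-arm test or estimate; the only test of change is before versus after induction

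*Combined protocol and SAP*

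**What the plan says.** All references are to the combined protocol and SAP.

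- **Aim.** Section 14.3.1 (Background to A041701-LC1) plans plasma sE-selectin at baseline and after chemotherapy, with or without uproleselan, "to determine if E-selectin inhibition affects sE-selectin levels" and to relate levels to outcome.
- **Listed objective.** The only sE-selectin item in section 14.3.2 is "To examine the correlation of plasma soluble E-selectin concentrations with clinical outcomes". The drug-effect question is not listed there.
- **Test of change.** Section 14.3.3: "Secondary analysis will evaluate the sE-selectin expression level pre- vs. post-induction will be compared using two-sample t-tests or Wilcoxon rank-sum tests". Arm is not mentioned.
- **Content by arm.** Section 14.3.3 uses descriptive statistics and plots to "summarize both pre- and post-treatment E-selectin level to understand its distribution in each treatment arm". This carries over to the plasma marker through "Similar analyses will be conducted for sE-selectin".
- **Other sE-selectin analyses.** The same sentence carries over the remission versus non-remission comparison, the logistic models for CR, and the models for DFS, EFS and OS "using Cox regression model, stratified by treatment arm". None of these estimates an effect of arm on sE-selectin.
- **Contrast within the substudy.** For MRD, section 14.3.4 does plan a chi-square comparison of rates by treatment arm.

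**The concern.** Whether adding uproleselan changes sE-selectin is a comparative question, and a randomized control arm is available to answer it. Allocation is 1:1 (section 13.1), and the table in section 6.2 schedules LC1 plasma at pre-registration and at end of induction for both arms.

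The protocol gives reasons to expect movement with no drug effect. Section 14.3.1 links leukemia and chemotherapy to greater E-selectin expression and shedding. Section 1.2 reports raised levels in newly diagnosed AML and states that "decrease in sE-selectin levels correlated with durable remission of AML". Both arms have leukemia, receive 7+3 and contain remitters. A before/after test, paired or unpaired, pooled or run within the uproleselan arm, measures all of these together.

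Two things are at stake. A significant change could appear when uproleselan does nothing to the marker. A true difference between the arms would have no prespecified estimate or interval.

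**Working it through.** **1. The plan's own figure.** Section 14.3.3 gives 88% power for a 0.3 SD difference in baseline E-selectin expression, 375 remitters against 161 others (536 − 375), two-sided 0.05.

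- Standard error in SD units: √(1/375 + 1/161) = 0.0942.
- Power: Φ(0.3/0.0942 − 1.96) = Φ(1.22) = 0.89; the noncentral t gives 0.888.

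The figure reproduces, but it belongs to a responder comparison. No power is given for the pre/post test or for any arm contrast on sE-selectin.

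**2. Inputs for the illustration.**

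- From the documents: section 14.3.4 expects about 200 evaluable Phase II patients in the substudy, so about 100 per arm. Section 13.1.1 says there is no further Phase III accrual, so this is the relevant size.
- Assumed: 80 to 100 per arm with both samples; the same shift δ of 0.3 to 0.5 SD in both arms; pre/post correlation ρ of 0 to 0.7; drug effect zero. The documents give no SD, shift or correlation for sE-selectin.

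**3. Planned two-sample test, arms pooled.** With n samples at each time, the statistic has mean δ√(n/2) and, because each patient contributes to both groups, variance 1 − ρ. The chance of significance is about Φ[(δ√(n/2) − 1.96)/√(1 − ρ)].

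| n per time | δ (SD) | ρ = 0 | ρ = 0.5 | ρ = 0.7 |
|---|---|---|---|---|
| 160 | 0.3 | 76.5% | 84.7% | 90.7% |
| 160 | 0.5 | 99.4% | >99.9% | >99.9% |
| 200 | 0.3 | 85.1% | 92.9% | 97.1% |
| 200 | 0.5 | 99.9% | >99.9% | >99.9% |

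For example, with n = 160, δ = 0.3 and ρ = 0: 0.3 × √80 = 2.683, and Φ(2.683 − 1.96) = Φ(0.723) = 0.765.

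**4. Same test with no net shift (δ = 0).** Both tails give 2[1 − Φ(1.96/√(1 − ρ))]: 5.0% at ρ = 0, 0.6% at ρ = 0.5 and 0.03% at ρ = 0.7. Ignoring the pairing makes the test conservative here.

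**5. Simulation check** (100 per arm, ρ 0.3 to 0.7, 1,500 runs per setting, no drug effect). At 0.3 SD, the two-sample pre/post test is significant in 89–97% of trials pooled and 56–61% within the uproleselan arm alone. At 0.5 SD the figures are about 100% and 97–99.5%. A between-arm comparison of change stays at about 4–7% throughout.

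**6. What a baseline-adjusted arm comparison could detect.** Detectable difference at 80% power = 2.8 × √[(2/m)(1 − ρ²)], with m patients per arm.

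- m = 80: 0.44 SD at ρ = 0; 2.8 × √(0.025 × 0.75) = 0.38 SD at ρ = 0.5.
- m = 100: 0.40 SD at ρ = 0; 0.34 SD at ρ = 0.5; 0.28 SD at ρ = 0.7.

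**The case against.** The case for leaving the text alone has five parts.

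- **Status of the aim.** It is a clause in a background section. The objectives in section 14.3.2 are headed exploratory and list only correlation with outcomes for sE-selectin. No trial decision or alpha depends on it. This stands and limits the consequence.
- **The arms are described.** A reader might infer that the plan never sets the arms side by side. That is too strong: section 14.3.3 plans summaries and plots in each arm, so an informal comparison is possible. What is missing is a test or an estimate with an interval.
- **The sentence on the test is garbled.** Two-sample methods suit independent groups, so comparing change between arms might have been intended. The wording does not support that reading: the contrast it names is pre- versus post-induction.
- **Interpretation.** A reader might also infer that a pre/post change would be reported as a drug effect. The plan states no such rule. Section 1.3 does read a fall in plasma sE-selectin as on-target activity, but in an earlier open-label dose-escalation phase where every patient received uproleselan. The risk is plausible; the outcome is not documented.
- **Size.** Chemotherapy may raise sE-selectin while remission lowers it, so the net shift could be near zero, and then the test seldom rejects. Where it does reject because of a shift, it detects a true change over time; that becomes an error only if attributed to uproleselan. Both points stand, which is why the figures are an illustration and not a forecast.

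**Conclusion.** The concern holds as a mismatch between a stated aim and its analysis. Section 14.3.1 poses a drug-effect question; section 14.3.3 provides no between-arm test or estimate, and its only test of change cannot distinguish uproleselan from leukemia, chemotherapy or remission. The MRD comparison by arm in section 14.3.4 suggests an oversight, not a policy against arm comparisons in the substudy.

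Under the assumed conditions, the pooled pre/post test is significant in about 77% to nearly 100% of trials with no drug effect, and in 5% or fewer if there is no net shift. The range depends on the assumed 80 to 100 pairs per arm, equal shift and correlation.

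The effect is confined to an exploratory correlative conclusion. Nothing here touches the EFS or OS analyses. This is a cheap improvement.

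**What to change.** In section 14.3.3, specify for this aim a between-arm comparison of log end-of-induction sE-selectin: linear regression on randomized arm, adjusted for baseline sE-selectin and the stratification factors (age group, performance status, de novo versus secondary/therapy-related AML), reported as the arm ratio with a 95% CI. Keep pre/post change as description.

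**Cost.** A sentence or two of analysis text and one regression. The samples are already scheduled, so no new patients, samples or assays are needed.

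**Downside.** Patients with both samples are selected after randomization: they must survive to the second draw and provide it, and section 1.1 cites early mortality of up to 20% with 7+3 in older adults. Report the number and reasons for missing post-induction samples by arm. Describe the result as the effect of adding uproleselan among sampled patients. Any difference may act partly through remission, so it should not be presented as E-selectin inhibition in isolation.
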